10.2.1.1 Study visit: Month 6 (Day 169 \pm 3 days)

After all Month 6 assessments pertaining to the main study have been made and the subject has been confirmed to be eligible to proceed in the extension study (see section 9.2), the subject will be requested to sign the extension-specific ICF that she was given at the Month 5 visit.

Note: inclusion in the extension study will not be postponed if the results of any Month 6 assessment are not available on the day of Month 6 visit. Subjects will be required to stop the treatment if the results obtained after enrollment meet the discontinuation criteria defined in Section 10.7.2.1.

After signature of the extension-specific ICF, the subject will be dispensed new treatment kits. The subject will take her daily dose of study medication at the study site from these newly dispensed kits. The exact time of dosing (hour/minute) will be recorded in eCRF.

In addition, the subject will:

- receive contraception counselling and will be given double barrier contraception (condoms with spermicide), if requested, to be used until 3 months after treatment end. If the subject is at risk for

acquiring HIV, she must be reminded to use double non-hormonal barrier contraception without spermicides (eg: condoms and diaphragms).

- be provided/prescribed a limited quantity (as per Investigator's judgement) of standard doses of permitted analgesics as rescue medication for EAP for the duration of the study.
- receive calcium 500 to 1000 mg and vitamin D 400 IU supplementation

Upon completion of the visit, the subject will be provided with emergency contact phone numbers and will be scheduled for her next visits.

10.2.1.2 Study visits: Month 7 (Day 197 -3/+2 days) and Month 8 (Day 225 ± 3 days)

The following tests and evaluations will be performed :

- eDiary completion compliance check
- ePRO and ClinRO completion, ideally before any other procedures or assessments:
 - at Month 7 visit: EHP-30, EQ-5D-5L, PROMIS, mPGIS, PGIC, HRUQ, HRPQ with mPGIS and PGIC completed last
 - at Month 8 visit: mPGIS, PGIC, HRUQ and HRPQ with mPGIS and PGIC completed last.
- Concomitant treatments recording
- AE recording
- Completion of the paper C-SSRS questionnaire (version for "already enrolled subjects" (see Appendix S) for patients responding to the C-SSRS for the first time during the study, or version "since last study visit" (see Appendix T) for patients for whom the C-SSRS was completed at the previous study visit)

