10.4.5 Endometrial biopsies

At the end of the Treatment Period (i.e. at Month 12 visit), endometrial biopsy for histological assessment will have to be obtained for each subject unless the endometrium thickness in TVUS is \leq 5 mm, in which case no endometrium biopsy will be necessary (

Figure 3).

[figure not shown]

Figure 3 : Biopsy process for Month 12 visit

During the Follow-Up Period, the schedule for endometrial biopsy is as described in Figure 4 below.

[figure not shown]

Figure 4 : Biopsy process for the Follow-Up Period visits

The endometrial biopsies will be analyzed by a central laboratory blinded to treatment group. Endometrial biopsies of hyperplasia of any type will be submitted for assessment by three independent expert pathologists who are blinded to the treatment and to one another’s assessment.

At any time during the study, in case of endometrial biopsy diagnosis being hyperplasia of any type (with or without atypia) or worse (neoplasm) for patient on treatment, the laboratory will send an alert to the site and the Sponsor. The medical monitor will contact the sites to discuss the proceeding in line with local practice. The subject will be discontinued from the treatment, will enter the follow-up period and will be advised to consult for gynecological evaluation and treatment.

Biopsy should be recommended (for cause) for subjects with heavy/suspicious bleeding. Results from these procedures should be documented in the eCRF.

Endometrial biopsy samples will be performed with the Pipelle de Cornier® (or equivalent), as described in the manual provided by the central laboratory.

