10.7.2 Subject Withdrawal

Subjects will be informed that they have the right to withdraw from the study at any time, without prejudice to their medical care, and that they are not obliged to state the reason(s). Any withdrawal must be fully documented in the eCRF exit form.

The Investigator may withdraw a subject at any time if this is considered to be in the subject's best interest.

In addition, the Sponsor could make a decision to temporarily or permanently discontinue the study for safety, ethical, compliance or other reasons. In this case, the subject's participation may be ended prematurely without asking for her consent.

In case of early discontinuation, the subject will be instructed to complete the relevant eDiary questionnaires as soon as possible upon treatment discontinuation.

Withdrawal during Treatment Period:

Subjects discontinuing participation in the study during the Treatment Period should undergo the procedures required at Month 12, except the DXA in case of discontinuation before Month 9 visit. These subjects will enter the 6-month Follow-Up Period and will continue daily eDiary recording for 6 months and up to Month 6 ExFU visit in order to continue to collect efficacy and safety data.

PK sampling is not required if the subject had no IMP administration the day prior to the withdrawal visit.

Withdrawal during Follow-Up Period:

Subjects discontinuing participation in the study during the Follow-Up Period should undergo the procedures required at Month 6 ExFU visit, which includes completion of all ClinRO and ePRO questionnaires, except the DXA in case of discontinuation before Month 3 ExFU visit.

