5.2. Data Conventions

5.2.1. Last extension treatment administration date, End of extension Study date and Period definitions

The last extension treatment administration date will be defined as the date from the treatment termination reported in the extension period eCRF page. If this date is missing, the last date with a drug intake in the eDiary that is inferior or equal to Month 12 visit or the last available date with a drug intake in the eDiary if the subject discontinued the extension treatment will be used.

For subjects who entered the extension, the end of the extension study date will be the last assessment date in the extension study defined as last assessment recorded in the eCRF (excluding end date of adverse events and concomitant medications) or ediary date (excluding drug intakes recorded after last extension treatment administration date). This will not necessarily be the same date as last assessment date as recorded in the eCRF.

For each 28-day period prior to Month X (except Month 12), the end of the period will be defined as the Month X visit date. If subject discontinued prior to Month X, the end of the period will be the date from the treatment termination of extension period eCRF page or the last date with a drug intake in the eDiary if missing. If the subject missed the Month X visit (but did not discontinue), the subject might still have filled the diary during that time: the theoretical Month X date will be used to define the end of the 28-day period. The theoretical Month X is defined with respect to Day 1 as Month X= Day 1+ $28^{*}X$.

For the 28-day period prior to Month 12, the end of the period will be defined as the last extension treatment administration date.

Note:

For Adverse Events, Concomitant Medications and Daily diaries data collected on the Month 6 date will be part of the extension for subjects entering the extension study.

For Adverse Events, Concomitant Medications and Daily diaries, data collected on the Month 12 date will be part of the Extension Follow-up period for subjects entering the Extension follow-up period.

The extension treatment period will be defined as Month 6 up to (Month 12 date -1) or treatment discontinuation date.

The extension follow-up period will be defined as the Month 12 date or (treatment discontinuation date+1) up to the extension follow-up end date (for subjects who entered the extension follow-up).

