For other safety data, data from early discontinuation should be compared to theoretical visits dates. Only assessments within the window of theoretical date +/-14 days will be used for analyses, if it is planned to have a such assessment at this visit and no other assessment is in the window. If a subject discontinued in the extension treatment period, date will be compared to the theoretical visit dates in extension treatment period as described in Table 1. If a subject discontinued in the extension follow-up period, date will be compared to the theoretical visit dates in extension follow-up period, date will be compared to the theoretical visit dates in extension follow-up period, date will be compared to the theoretical visit dates in extension Follow-up period from Table 2.

For unscheduled safety assessments, if the assessment occurs within a window of theoretical date +/- 14 days for a planned eCRF visit for which it was planned per protocol to have such assessment, and no assessment was done for that visit, the assessment will be assigned to that visit. If the assessment is equally distant from two eCRF visits with no corresponding safety assessment, the assessment will be assigned to the next visit.

For biopsy, DXA assessment or laboratory assessment, if an assessment has been assigned in external data to a follow-up visit of the main study for subjects who entered in the extension study, the visit of assessment should be reassigned with the same rules described above for unscheduled safety assessment.

Visit	Theoretical Date
Month 6	Day 169
Month 7	Day 197

Table 1 Theoretical Visit Dates in Extension Treatment Period

CRS-BS-TP-000005 V 2.0

Page 29 of 99

Kissei / Cytel Confidential: This is a controlled document and shall not be changed, saved, copied or reproduced by any unauthorized person.

Month 8	Day 225
Month 9	Day 253
Month 10	Day 281
Month 11	Day 309
Month 12	Day 337

Table 2 Theoretical Visit Dates in Extension Follow-up Period

Visit	Theoretical Date
Month 1 ExFU	Month 12 or treatment discontinuation date + 28
Month 3 ExFU	Month 12 date or treatment discontinuation date + 84
Month 6 ExFU	Month 12 date or treatment discontinuation date + 168

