6.6.8.1. Endometrial biopsy

Biopsies for histological assessment were obtained for each subject at the following timepoints:

- Month 6 or one at Month 12 if endometrium thickness via TVUS is > 5 mm
- Month 1 ExtFU, 3 ExtFU, or 6 ExtFU if not obtained at Month 12 or if the preceding biopsy diagnosis is different than "benign endometrium"

For biopsies with reported primary diagnosis "Hyperplasia" or "Malignant Endometrial Neoplasm" at other visits than screening, a second read of the biopsy was to be performed. If the diagnosis of the two reads was different, then the sample was to be re-read a 3rd time. In case of multiple readings, the following rules will be applied for the statistical analysis:

- If 2 readings out of 3 lead to the same diagnosis, one of these 2 records will be selected.

- Otherwise, the record corresponding to the most severe diagnosis should be selected considering the following order, from less severe to more severe: simple without Atypia hyperplasia < complex without Atypia hyperplasia < simple with atypia hyperplasia < complex with Atypia hyperplasia < other malignant neoplasm.

In addition, in order to perform a quality check of the readings, 15% of biopsies were sent blinded for a second read when the primary diagnosis was "Benign Endometrium". In case of multiple readings when the primary diagnosis from the first read is "Benign Endometrium", this first read will be used for the analysis. Biopsies with a primary diagnostic 1 "Benign Endometrium" will be analyzed in the classification "Benign Endometrium without Hyperplasia or Atypia".

A summary at each time point will be performed (number and percentage of subjects with normal, abnormal, not assessable).

Biopsy assessment will be summarized by classification (primary diagnosis 1) and primary diagnoses (diagnoses 2, 3 and 4) at each visit. Subjects will be counted only once for classification (primary diagnosis 1) and a subject could be in several diagnoses (e.g. if for example diagnoses 2 and 3 are fulfilled).

Possible results by classification (primary diagnosis 1) and primary diagnoses (diagnoses 2, 3 and 4) are:

- Benign Endometrium without Hyperplasia or Atypia: Proliferative, Atrophic, Metaplastic Changes, Secretory, Indeterminate, Inactive, Polyp, Endometritis, Menstrual phase, Other
- Hyperplasia: Simple with Atypia, Simple without Atypia, Complex with Atypia, Complex without Atypia
- Malignant Endometrial Neoplasm: Carcinoma, Sarcoma, Other Malignant.

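### The ±14-day rule keeps early-withdrawal biopsies on Days 184–322 out of the by-visit histology tables, so hyperplasia found on treatment can be missing from the histology endpoint

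*SAP*

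**What the plan says.** SAP 5.5, under other safety data, has two rules.

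- **Early discontinuation.** "Only assessments within the window of theoretical date +/-14 days will be used for analyses, if it is planned to have a such assessment" at that visit, and only if the window holds no other assessment. The reference dates are fixed: "If a subject discontinued in the extension treatment period, date will be compared to the theoretical visit dates in extension treatment period", which are those of Table 1.
- **Unscheduled assessments.** If one lies within 14 days of a visit at which that assessment is planned, "and no assessment was done for that visit, the assessment will be assigned to that visit". The SAP does not say what happens to an assessment that matches no visit.

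The schedule of assessments in both documents (Protocol Appendix A, SAP Appendix F) puts treatment-period biopsies at Months 6 and 12 only, and no biopsy is needed if the endometrium is 5 mm or thinner.

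The protocol generates biopsies at other times. Section 10.7.2: "Subjects discontinuing participation in the study during the Treatment Period should undergo the procedures required at Month 12"; the only exemption is DXA for withdrawals before Month 9. Section 10.4.5: "Biopsy should be recommended (for cause) for subjects with heavy/suspicious bleeding". Hyperplasia or worse obliges the woman to stop treatment (10.4.5 and 10.7.2.1).

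On reporting, SAP 6.6.8.1 says: "Biopsy assessment will be summarized by classification (primary diagnosis 1) and primary diagnoses (diagnoses 2, 3 and 4) at each visit". It has no any-time or worst-diagnosis row. Individual biopsy results, including multiple readings, are listed.

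**The concern.** The safety endpoint (Protocol 7.2, SAP 3.3) covers any pathological endometrial change from baseline on histology and is not limited to Month 12. Biopsies taken for bleeding, or at a withdrawal, are a plausible place for such a change to show. If they have no slot in a by-visit table, the histology result describes mainly women who reached Month 12.

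Take a woman whose withdrawal biopsy in mid-treatment shows hyperplasia. Protocol 10.2.2.1 calls for a Month 1 follow-up biopsy whether her withdrawal biopsy counts as the Month 12 biopsy (it was not benign) or does not (none was then done at Month 12). If that off-treatment sample is benign, it is her only tabulated histology after Month 6.

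The SAP avoids this problem elsewhere. Section 6.6.3 takes the worst on-treatment value for liver tests, unscheduled samples included, and counts progesterone above 10 nmol/L at least once from Month 6 to Month 12. Section 6.6.8.4 counts C-SSRS events at any time after baseline.

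**Working it through.** **Inputs.** SAP 5.2.1: "The theoretical Month X is defined with respect to Day 1 as Month X= Day 1", to which 28 × X is added. Window half-width: 14 days (SAP 5.5). Planned biopsies: Months 6 and 12. Last dose: the day before the Month 12 visit (Protocol 10.2.1).

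**Reproducing the plan's dates.**
- Month 6: 1 + 28 × 6 = Day 169.
- Month 12: 1 + 28 × 12 = Day 337.

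Both agree with SAP Table 1.

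**Windows.**
- Month 6: 169 ± 14 = Days 155–183.
- Month 12: 337 ± 14 = Days 323–351.

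**Gap.**
- Uncovered days: 184 to 322, so 322 − 184 + 1 = 139.
- Treatment days: 169 to 336, so 336 − 169 + 1 = 168.
- 139 / 168 = 82.7%.

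**Effect of the condition on other assessments.** If a Month 6 biopsy exists, that window is already taken and the gap runs from Day 170 to Day 322: 153 days, 153 / 168 = 91.1%. If none exists, a withdrawal biopsy on Days 170–183 would be tabulated as Month 6.

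**Unscheduled biopsies after treatment stops.** SAP Table 2 dates follow-up visits from the stop date (+28, +84, +168 days), so some of these do find a slot. For a stop on Day 200:
- Month 1: 228 ± 14 = Days 214–242.
- Month 3: 284 ± 14 = Days 270–298.
- Month 6: 368 ± 14 = Days 354–382, beyond the gap.

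That covers 29 + 29 = 58 of the 139 gap days. For a stop on Day 309 it covers none. The route does not help biopsies taken on treatment, nor the withdrawal-visit biopsy, which is compared with Table 1.

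**How many women?** The documents give no withdrawal, for-cause biopsy or hyperplasia rate. As an illustration only, assume that 5% to 20% of the planned maximum of 288 entrants withdraw, evenly over time:
- 5%: 288 × 0.05 × 139/168 = 11.9 visits in the gap.
- 20%: 288 × 0.20 × 139/168 = 47.7 visits in the gap.

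These are visits, not biopsies; women with an endometrium of 5 mm or less have no biopsy.

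**The case against.** The strongest reply is that the cases are not lost.

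- **Adverse events.** Under Protocol 12.1.2, an abnormality that stops study drug, or that suggests disease not present at main-study screening, meets an AE criterion. Starting on treatment or within 30 days after, it is a TEAE (SAP 6.6.1) and is counted overall, by system organ class and preferred term, and among TEAEs that ended treatment. All biopsy results are also listed. This stands, so a reader who infers that such hyperplasia vanishes from every table goes too far. But AE reporting rests on the investigator's assessment and coded term. It does not use the multi-reader diagnosis rule of 6.6.8.1 and has no denominator of biopsied women.
- **For-cause biopsies.** The restrictive sentence governs early-discontinuation data only. This also stands. The loss of for-cause biopsies is an inference: they match no visit, and the tables are by visit.
- **Hyperplasia on the Month 6 biopsy.** If the result arrives after enrolment, the sample still lies in the Month 6 window, and the Extension Safety Analysis Set keeps the woman. Correct; the gap concerns later biopsies.
- **Persistent pathology.** It would show again in a follow-up biopsy. Correct; what the histology tables miss is pathology that has gone by then.
- **General visit rule.** SAP 5.5 opens by using visits as recorded in the eCRF, so a withdrawal visit might seem to stand on its own. The specific rule for early-discontinuation data displaces that.

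**Conclusion.** The point holds for the histology tables. By explicit text, withdrawal biopsies on Days 184–322 (from Day 170 where a Month 6 biopsy exists) are not used in them. By inference, for-cause biopsies taken on treatment in that span have no place in them. Hyperplasia found on treatment can therefore be missing from the histology endpoint, and a benign follow-up sample may stand as that woman's only tabulated result after Month 6.

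Two stronger readings are tempting and unsupported. First, 82.7% is a share of calendar days. Scheduled biopsies cluster at Months 6 and 12, so it does not mean that most biopsies are lost, and the number affected cannot be derived. Second, the bias need not always favour safety. Omitting a hyperplasia case lowers the reported percentage, but omitting a benign withdrawal biopsy shrinks the denominator and raises it. Whether a woman with a benign withdrawal biopsy is biopsied again is unclear, because the protocol does not say if that sample counts as the Month 12 biopsy.

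The study is descriptive, with no hypothesis tests. What is at stake is completeness: if hyperplasia is rare, one omitted case could change a group's tabulated count from one to zero.

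**What to change.** In SAP 6.6.8.1 add one summary, by treatment group on the Extension Safety Analysis Set: the most severe biopsy diagnosis after Month 6, counting scheduled, unscheduled or for-cause, and early-withdrawal biopsies.

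- **Denominator:** women with at least one such biopsy.
- **Periods:** show on-treatment and follow-up separately. State that Month 12 and withdrawal-visit biopsies count as on-treatment, because the period definitions in 5.2.1 place the Month 12 date, and days after the stop date, in follow-up.
- **Severity:** use the order already in 6.6.8.1, with benign at the bottom and the places of carcinoma and sarcoma stated.
- **SAP 5.5:** exempt biopsies from the window and planned-visit conditions for this summary, and say what happens to unscheduled assessments that match no visit.

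The by-visit tables can stay as they are. The cost is one extra table from data already collected, and the reported incidence may be slightly less favourable. No trial procedure changes.

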Median Z scores, interquartile ranges and total ranges for femoral neck, total hip and lumbar spine at baseline, Week 24 and Week 52 did not change importantly over time: medians remained within the range of -0.20 to 0.30, 0 to 0.40, and -0.25 to 0.35 in all treatment groups for the femoral neck, total hip and lumbar spine, respectively. Median absolute change from baseline to Week 52 ranged from -0.10 to 0.00, -0.10 to 0.00 and -0.20 to -0.10, respectively.

Over the 52-week treatment period, 154/176 (87.5%) of subjects reported treatment emergent adverse events (TEAEs). The incidence of TEAEs was not dose-dependent across treatment groups, ranging from 81.8% in the 100 mg group to 93.3% in the 200/100 mg group. The majority of the TEAEs (616/846; 72.8%) were reported during the first 24 weeks of treatment.

The most commonly reported TEAEs were headache (32.4%) and hot flush (28.4%). The majority of these events occurred during the first 24 weeks of treatment. Headaches were reported with a similar frequency across treatment groups, ranging from 22.2% in the 75 mg FD group to 44.8% in the placebo/100 mg group, with no apparent dose relationship. Conversely, the incidence of hot flushes was dose-dependent and increased with increasing exposure to linzagolix: 16.7% (50 mg), 20.7% (75 mg FD), 22.2% (75 mg TD), 24.1% (placebo/100 mg), 27.3% (100 mg), and 60.0% (200/100 mg). Of note, there was no worsening in the incidence of hot flushes during the treatment extension; only 2/61 hot flush events were reported.

Ten serious AEs (SAEs) were reported in nine subjects. None of the SAEs were considered as related to study treatment. The SAEs of ruptured ectopic pregnancy (50 mg), pelvic pain (50 mg), pneumonia (75 mg TD), and anxiety disorder (200/100 mg) led to subject withdrawal from treatment during the extension phase of the study.

During treatment extension, 12 subjects (6.8%) reported 17 TEAEs leading to treatment withdrawal. In the 200/100 mg group, one subject discontinued treatment due to bone loss and one subject due to bone pain. In the 75 mg FD group, one subject discontinued treatment due to bone density decreased.

There were no subjects with AST and/or ALT values $>2 \times$ ULN during the treatment extension.

Overall, there were no clinically meaningful changes from baseline in laboratory parameters, vital signs, physical examination, or lipid measurements including HDL cholesterol, LDL cholesterol, and triglycerides in any group.

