10.2 OUTLINE OF STUDY PROCEDURES AND ASSESSMENTS

The first visit for this extension study is combined with the Month 6 visit of the main study. Therefore, the Month 6 assessments from the main study will not have to be duplicated at the start of the extension study. The study visit schedule is depicted in Figure 2 and the schedule of assessments is detailed in Appendix A and Appendix B.

* At the end of the 6-month follow-up, subjects with a BMD decrease from baseline of > 1.5% for lumbar spine and/or > 2.5% for total hip compared to main study baseline will have an additional DXA scan 6 months later.

Figure 2 : Schedule of Visits

All visits should take place at the end of the defined period (i.e. Month 7 visit should be scheduled at the end of Month 7, Month 8 visit should be scheduled at the end of Month 8, etc.). One month is defined as 28 days/4 weeks. All visit dates are calculated from the date the patient started treatment in the main study (Day 1 visit of 18-OBE2109-003 Edelweiss 3):

- Month 7 (Day 197), Month 8 (Day 225), Month 9 (Day 253), Month 10 (Day 281), Month 11 (Day 309) and Month 12 (Day 337) for the Treatment Period,
- Month 1 Extension FU (Day 365), Month 3 Extension FU (Day 421) and Month 6 Extension FU (Day 505) for the Follow-up Period.

A window of -3/+2 days is allowed for Month 7 visit, and of ± 3 days for each of the following visits during the Treatment Period. A window of ± 7 days/1 week is allowed for each visit scheduled during the Follow-Up Period.

The timing of events is shown in the Schedule of Assessments (Appendix A and Appendix B).

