6.6.4. Vital Signs and Physical Examinations

Vital signs include: Height (cm), Weight (kg), Body Mass Index, Systolic Blood Pressure (mmHg), Diastolic Blood Pressure (mmHg) and Heart Rate (beats/min).

Height is assessed at Screening (main study); Weight is assessed at Month 6, Month 9, Month 12, as well as at M3 ExtFU and M6 ExtFU visits. Other Vital Signs are assessed at every monthly visit during the extension treatment period and at Month 1, 3 and 6 from the extension follow-up period.

Physical Examination was to be assessed Month 6, Month 9, Month 12, as well as at M3 ExtFU and M6 ExtFU visits.

The actual value, change from baseline and change from baseline 2 (only for the subjects who are in the placebo arm in the main study) for each on-study evaluation will be summarized by treatment group for vital signs.

By-subject listings of vital sign measurements will be presented in data listings.

Physical examination results at each time point will be summarized by treatment group; Shifts from Baseline and shift from baseline 2 (only for the subjects who are in the placebo arm in the main study) in physical examination findings to each on study visit will also be presented.

All physical examination findings will be presented in a data listing.

6.6.5. **Electrocardiogram**

Local 12-lead ECG readings of QTcF are performed at every monthly visit during the extension treatment period, as well as Months 1,3 and 6 from the extension follow-up period.

Baseline will be defined as the highest QTcF value prior to first dose of the main study.

Baseline 2 will be defined as the highest QTcF value prior to first active dose of the extension study from screening to Month 6 (only for subjects in the placebo arm of the main study).

The actual value, change from baseline and change from baseline 2 (only for the subjects who are in the placebo arm in the main study) of ECG results will be summarized descriptively, as well as the number and percent of subjects with normal, abnormal and clinically significant abnormal results at each study visit by treatment group.

All ECG data for each subject will be provided in data listings.

6.6.6. **Concomitant Medications**

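### SAP 5.5 leaves a withdrawal ECG, vital-sign or routine laboratory result out of every by-visit table if it falls 1–13 days after an attended visit, and outside the liver panel no other summary of values includes it

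*SAP*

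**What the plan says.** Protocol 10.7.2 asks for a full assessment when a woman stops early: "Subjects discontinuing participation in the study during the Treatment Period should undergo the procedures required at Month 12", with an exception only for DXA before Month 9. The Month 12 list includes ECG, vital signs, haematology, coagulation and chemistry.

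SAP 5.5, under other safety data, limits how these results are used. "Only assessments within the window of theoretical date +/-14 days will be used for analyses", and then only "if it is planned to have a such assessment at this visit and no other assessment is in the window". An assessment must therefore be near a theoretical visit, be scheduled at that visit, and find the window empty.

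The summaries in SAP 6.6.3 to 6.6.5 are organised by visit. For ECG, SAP 6.6.5 plans values, changes and the "number and percent of subjects with normal, abnormal and clinically significant abnormal results at each study visit by treatment group". None of these sections plans an end-of-treatment or last-on-treatment row. Only the liver parameters (ALT, AST, ALP, total bilirubin, albumin) also have a shift to the worst on-treatment value that counts unscheduled results.

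**The concern.** The withdrawal assessment is the one closest to the decision to stop. A woman who attends a visit and withdraws within the next 13 days has her withdrawal result in a window that the scheduled result already occupies. The tables then show the earlier value and omit the later one.

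QT prolongation and laboratory safety are stated objectives (Protocol 6.2). Calcium shows how this could matter. Protocol 10.7.2.1 calls for a fasting repeat within two weeks of a high value and bases definitive discontinuation on it. If the first value came from a scheduled visit, a repeat 1–13 days later falls in the filled window, and calcium has no worst-value table.

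The SAP treats questionnaires differently. They are under the same filled-window rule in SAP 5.5, but SAP 6.4.3 adds a second summary that carries discontinuation-visit values to later scheduled visits. Safety data have no counterpart.

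**Working it through.** **Inputs.**
- Visit spacing, Protocol 10.2: "One month is defined as 28 days/4 weeks".
- Theoretical dates, SAP Table 1: Days 169, 197, 225, 253, 281, 309, 337. These reproduce from Day 1 + 28X: 1 + 28×6 = 169 and 1 + 28×12 = 337.
- Window: ±14 days (SAP 5.5). Permitted visit deviation: ±3 days (−3/+2 at Month 7), so an attended visit lies in its own window.
- Planned entry: 450 × 0.8 × 0.8 = 288.
- Phase 2b extension, Protocol 5.5.3: "12 subjects (6.8%) reported 17 TEAEs leading to treatment withdrawal" (12/176 = 6.8%).

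Neither document states what share of withdrawal values will be used, so there is no plan figure to reproduce.

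**Step 1: the rule for monthly items.** Let the last attended visit be on its theoretical day V and the withdrawal assessment on V + k.
- k = 1 to 13: the next visit is 28 − k ≥ 15 days away. Only V's window applies, it is filled, and the result is not used.
- k = 14: the day lies in both windows. It is counted here as used in the next, empty one, but the SAP does not say so.
- k = 15 to 27: only the next, empty window applies, and the result is used.

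Example: Month 9 attended on Day 253, withdrawal on Day 262. The Month 9 window is Days 239–267 and the Month 10 window is Days 267–295, so the Day 262 result is unused.

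**Step 2: share under even timing.** Each interval loses 13/27 = 48.1%. Over six intervals this is 6×13 = 78 of 6×27 = 162 days. If day 14 is also lost, it is 84/162 = 52%. Counting scheduled visit days as possible withdrawal days gives 78/168 = 46%. Simulating visit dates with ±3 days of variation gives 48%.

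**Step 3: other timing.** All rows are assumptions.

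| Assumption | Share unused |
|---|---|
| Clustered soon after a visit, Beta(1,2) to Beta(1,3) | 73% to 86% |
| Clustered late in the interval, Beta(2,1) to Beta(3,1) | 24% to 12% |
| Half withdraw on a scheduled visit date: 0.5 × 13/27 | 24% |
| Preceding visit missed in 10% to 20% | 43% to 38% |
| Even stopping, withdrawal visit 3 days later: 10/27 | 37% |
| Even stopping, withdrawal visit 7 days later: 6/27 | 22% |
| Extremes: all on days 14–28, or all on days 1–13 | 0%, 100% |

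**Step 4: quarterly items.** Weight, and lipids on the protocol schedule, are planned at Months 6, 9 and 12. A between-visit result is used only on Days 239–252 or 323–336, which is 28 of 162 days. The other 134 (83%) are unused under even timing. Many of these fail the second condition, that the item be planned at that visit.

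**Step 5: number of women.** 0.068 × 288 = 19.6 withdrawals for adverse events, and 19.6 × 13/27 = 9.4. With shares of 12% and 86% the count runs from 2.4 to 16.9.

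**Step 6: can another rule restore these values?** The unscheduled-assessment rule in SAP 5.5 also requires that nothing was done for that visit. The repeat-value rule in SAP 6.6.3 chooses within a study day and time, not between days. Neither helps.

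**The case against.** Several objections stand in part.

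- **Other capture exists.** SAP 6.6.3 to 6.6.5 list all laboratory, vital-sign and ECG data, with a subset listing of clinically significant laboratory values. Protocol 12.1.2 gives an abnormality that leads to stopping IMP as an example of a reportable adverse event. SAP 6.6.1 tabulates and lists TEAEs leading to discontinuation, and the DMC reviews unblinded safety data. This stands. But listings and event counts do not give group-level values or changes at stopping.
- **The tables match the endpoints.** Safety endpoints are mostly defined as change to each scheduled assessment, and nothing is tested. This also stands: the by-visit rows are not wrong, and the gap is a missing summary.
- **The numbers are small and borrowed.** The 6.8% comes from a Phase 2b extension with different regimens. About 9 women over four groups averages two or three per group. This limits the weight of the point.
- **Direction.** A reader might infer that the tables lean toward women and times without problems. The documents do not support that as a finding. Stopping triggered by a scheduled-visit result has its trigger value in that visit's table. Laboratory samples are read centrally, so the withdrawal value may be a later recheck, possibly off drug.
- **A last-value row can mislead.** It may pick a normalised recheck and hide the abnormal trigger. This stands and shapes the fix.

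**Conclusion.** The point holds as a property of the stated rule. For monthly assessments, a withdrawal result 1–13 days after an attended visit enters no by-visit table. For ECG, blood pressure, heart rate, haematology, coagulation and non-liver chemistry, including calcium, no other group-level summary of values includes it.

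The size depends on timing that the documents do not give. The 48% assumes withdrawal visits spread evenly between visits, the preceding visit attended, and no lag between stopping and the visit. A reader might take *about half are lost* as a fact of the plan. It is only the even-timing case, and it does not describe the quarterly items, where even timing gives about 83%. The estimate of about 9 of about 20 women also carries over the Phase 2b rate.

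Bias in the safety tables is possible but not shown. This is a worthwhile, inexpensive improvement to the safety reporting. It does not touch the efficacy analyses.

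**What to change.** In SAP 5.5 and 6.6.3 to 6.6.5, leave the by-visit rows as they are and add:

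1. To each ECG, vital-sign and laboratory table, an *End of extension treatment* row. It takes the last value on or shortly after the last extension dose, from any scheduled, withdrawal or unscheduled assessment. A limit of 7 days is one example; the sponsor should set it with the expected delay to the withdrawal visit in mind. Report the value, change from baseline, change from Baseline 2 where defined, and normal/abnormal category. State that the empty-window condition does not apply to this row.
2. For QTcF, calcium and other key parameters, a worst on-treatment summary that includes withdrawal and unscheduled results, following the method already planned for the liver parameters. This covers the case where the last value is a normalised recheck.

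Both use data already collected. The cost is SAP wording and some extra programming. For completers the end-of-treatment row repeats Month 12, and it mixes exposure durations, which a footnote should say.
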